Appendix 10. Child-Pugh Score

Measure	1 point	2 points	3 points
Total bilirubin, $\mu\text{mol/l}$ (mg/dl)	<34 (<2)	34-50 (2-3)	>50 (>3)
Serum albumin, g/L (g/dl)	>35 (>3.5)	28-35 (2.8-3.5)	<28 (<2.8)
PT INR	<1.7	1.71-2.30	>2.30
Ascites	None	Mild	Moderate to Severe
Hepatic encephalopathy	None	Grade I-II (or suppressed with medication)	Grade III-IV (or refractory)

Points	Class
5-6	A
7-9	B
10-15	C

Source:

1. Child CG, Turcotte JG (1964) "Surgery and portal hypertension". In Child CG. *The liver and portal hypertension*. Philadelphia:Saunders. pp. 50-64.

1. INTRODUCTION

This SAP is to describe the final analyses of data in evaluation of efficacy and safety of Study PCYC-1127-CA to support the Final CSR. The final analyses will be based on the final data extract. This SAP describes the additional analyses to the primary CSR SAP, dated 13 October 2017. All analyses that were performed previously for the primary CSR will follow the primary CSR SAP and will not be described again in this document. The additional analyses to support the Final CSR will be described in Section 2 (see summary in appendix Table 1).

2. ADDITIONAL ANALYSES

2.1. Progression-Free Survival after Subsequent Anti-neoplastic Therapy (PFS2)

Progression-free survival after subsequent anti-neoplastic therapy will be defined for all subjects in the ITT population as the duration of time from date of randomization to the date of the earliest of the following 3 types of events:

- PD per investigator response assessment after administration of the first subsequent antineoplastic therapy
- Death at any time on study due to any cause
- Initiation of a second subsequent anti-neoplastic therapy

For subjects randomized to placebo + rituximab arm, ibrutinib as next-line therapy will be considered as a subsequent anti-neoplastic therapy in the analysis of PFS2. Subjects who did not experience a PFS2 event will be censored at the later date of last available survival status and last adequate assessment. Subjects with no available survival status information and no adequate assessment after initiation of first subsequent anti-neoplastic therapy, will be censored at date of first subsequent anti-neoplastic therapy + 1.

Subjects without a baseline assessment, or with no adequate post baseline assessment and did not start first subsequent anti-neoplastic therapy, will be censored at the date of randomization.

The same methods used to analyze PFS will be used to analyze PFS2.

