3. STUDY DESIGN

3.1. Overview of Study Design

This is a randomized, placebo-controlled, double-blind, Phase 3 study designed to evaluate whether treatment with ibrutinib in combination with rituximab will result in an improvement in PFS compared to placebo in combination with rituximab in subjects with WM. In addition, an open-label ibrutinib substudy is included to further investigate the safety and efficacy of ibrutinib monotherapy in subjects with WM who are considered refractory to the last prior rituximab-containing therapy (refer to [Section 4.2](#)).

The study duration is estimated to be 4 years with approximately 1.5 years of enrollment and 3 years of follow up. The end of study will occur approximately 3 years after the last subject is randomized, or the Sponsor terminates the study, whichever comes first.

Approximately 150 subjects will be randomized in a 1:1 ratio to receive ibrutinib and rituximab (Treatment Arm A) or placebo and rituximab (Treatment Arm B).

Up to 30 subjects will be enrolled in the open-label ibrutinib monotherapy substudy (Treatment Arm C).

The study will include a Screening Phase, Treatment Phase and a Follow-Up Phase.

The Screening Phase assessments will be performed within 30 days prior to study treatment and will begin on the day the subject signs informed consent. During the Screening Phase, the subjects' eligibility will be determined. Eligible subjects must have clinicopathological diagnosis of Waldenström's macroglobulinemia (WM) confirmed by central pathology review and in accordance with the consensus panel of the Second International Workshop on WM ([Owen 2003](#)). Subjects with previously treated WM must have documented relapsed/refractory disease from their most recent prior therapy according to the modified WM consensus criteria. Further, subjects must have symptomatic disease meeting at least 1 of the recommendations from the Second International Workshop on Waldenström's Macroglobulinemia for requiring treatment. Subjects who meet all the inclusion/exclusion criteria are eligible to enter the study.

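### PFS2: subjects with no adequate post-baseline assessment and no subsequent therapy are censored at randomization even if known to be alive later, which is inconsistent with the general PFS2 censoring rule

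*SAP*

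**What the plan says.** Section 2.1 of the Final CSR SAP defines PFS2 from randomization to the earliest of three events:

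- progression, but only in this form: "PD per investigator response assessment after administration of the first subsequent antineoplastic therapy"
- death, with no restriction on timing: "Death at any time on study due to any cause"
- a further change of treatment: "Initiation of a second subsequent anti-neoplastic therapy"

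Three censoring rules follow.

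1. General rule: "Subjects who did not experience a PFS2 event will be censored at the later date of last available survival status and last adequate assessment".
2. A rule for subjects who started subsequent therapy but have no later information: "Subjects with no available survival status information and no adequate assessment after initiation of first subsequent anti-neoplastic therapy, will be censored at" the day after that therapy began.
3. A rule in its own paragraph. It covers subjects who were never assessed at baseline, and also those "with no adequate post baseline assessment and did not start first subsequent anti-neoplastic therapy, will be censored at the date of randomization".

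Appendix Table 1 of the same SAP repeats the PFS2 event definition but gives no censoring rule, so it does not settle how rules 1 and 3 relate.

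**The concern.** Rule 2 applies only when survival status is missing. Rule 3 has no such limit. Take a subject who is alive at the last contact, has no adequate post-baseline assessment and has started no new therapy. Rule 1 gives that subject a PFS2 time running to the last contact. Rule 3 gives zero. The text does not say which prevails, so two programmers could reasonably derive different values.

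If rule 3 prevails, event-free time that the trial has observed is left out. It is left out only for subjects who survive, because a death in the same group is a PFS2 event. Whether a subject stays in the risk set then depends on that subject's later outcome, and Kaplan-Meier and log-rank methods assume that it does not.

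**Working it through.** The plan states no event count, power or alpha for PFS2, so there is no PFS2 figure to reproduce. The check is logical first, then an illustration of size.

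**Which events are possible in this group?** Progression counts only after a first subsequent therapy. A second subsequent therapy cannot come before a first. For a subject who started none, only death remains. A survival contact therefore establishes event-free time, and no disease assessment is needed. In ordinary PFS progression counts from day 0, so event-free time cannot be shown without an assessment and censoring at randomization is reasonable. That argument does not carry over to PFS2 in this group.

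**Is the information collected?** Yes. Protocol 9.2 has all subjects followed for progression and survival after stopping treatment, whatever the reason. Protocol 8.4.1 records survival status and new anticancer therapy every 12 weeks. Protocol 8.4.2 adds survival sweeps at the interim analysis and at study closure.

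**How much time per affected subject?** Protocol 3.1 states: "The end of study will occur approximately 3 years after the last subject is randomized". At 12 subjects per month (Protocol 10.5), accrual takes 150/12 = 12.5 months, or 1.04 years. Potential follow-up is then 3 to 4.04 years. With the 1.5 years of enrollment given in Protocol 3.1 the upper end is 3 + 1.5 = 4.5 years. Rule 3 credits 0. These are maxima per subject on the planned timetable.

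**Effect on the estimate.** Assumptions, none from the documents except the arm size:

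- 75 subjects per arm, all otherwise followed for 3.5 years
- true 3.5-year PFS2 of S = 0.60 or 0.80
- k subjects in the rule 3 group, with the same risk as the rest
- deaths in that group counted, survivors censored at day 0.

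With no other censoring, the Kaplan-Meier estimate at 3.5 years is one minus deaths over those at risk after day 0. Putting in expected counts:

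estimate ≈ 1 − 75(1 − S) / (75 − kS)

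For k = 8 and S = 0.60 this is 1 − 30/(75 − 4.8) = 1 − 30/70.2 = 0.573.

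| k per arm (assumed) | S = 0.60 | fall (points) | S = 0.80 | fall (points) |
|---|---|---|---|---|
| 1 | 1 − 30/74.4 = 0.597 | 0.3 | 1 − 15/74.2 = 0.798 | 0.2 |
| 2 | 1 − 30/73.8 = 0.593 | 0.7 | 1 − 15/73.4 = 0.796 | 0.4 |
| 4 | 1 − 30/72.6 = 0.587 | 1.3 | 1 − 15/71.8 = 0.791 | 0.9 |
| 8 | 1 − 30/70.2 = 0.573 | 2.7 | 1 − 15/68.6 = 0.781 | 1.9 |

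A simulation with exponential times and 3,000 replicates gave 0.596, 0.594, 0.587 and 0.573 for S = 0.60, and 0.798, 0.795, 0.790 and 0.781 for S = 0.80. It agrees with the formula to within 0.001. When the survivors were instead censored at last known alive, the simulated estimates were 0.599 to 0.600 and 0.799 to 0.800, so the bias disappears.

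**The case against.** **Rule 3 may be a deliberate exception.** It sits in its own paragraph and names a special case, so it can be read as overriding the general rule. Each subject then has one censoring date. This is a fair reading, though the text does not state it. It removes the ambiguity but not the bias, because survivors are still set to zero while deaths count.

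**The group should be nearly empty.** Disease assessments start at Week 5 and repeat every 4 weeks (Protocol 8.3.3). Subjects who stop for reasons other than progression attend clinic every 12 weeks, with immunoglobulins and an overall disease assessment (Protocol 8.4.1). To be affected, a subject must have no adequate assessment at any of these visits, start no therapy, and still have known survival. The no-baseline limb should be rarer still, since eligibility requires measurable IgM and IgM is drawn at Screening and Week 1. This objection stands and limits the size of the point.

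**Stronger readings that the documents do not support.**

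- A reader might infer that early deaths are dropped, because rule 3 does not repeat that it concerns only subjects without an event. That would override the endpoint's own definition in the same section, which counts death at any time. The safer reading is that deaths count, and saying so removes the doubt.
- A reader might infer that everyone without a post-baseline assessment goes to day 0. In the post-baseline limb the rule reaches only those who also started no subsequent therapy. For the same reason a second subsequent therapy cannot be an event missed in that limb.
- A reader might infer that years of follow-up are lost across the trial, or lost unequally between arms. Years are a ceiling for each affected subject. The documents give neither a count nor any sign of imbalance.

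**Conclusion.** The point holds as a minor inconsistency. For event-free subjects with no adequate post-baseline assessment and no subsequent therapy, censoring at randomization discards known event-free time, conflicts with the general rule, and makes PFS2 slightly too low.

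The size depends on assumed counts. It is about 0.2 to 0.7 percentage points at 3.5 years for 1 or 2 subjects per arm, and about 2 to 3 points for 8, which is well above what the visit schedule makes likely. Similar counts in the two arms would shift both curves the same way.

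The argument assumes that deaths in this group are counted and that the subsequent-therapy record is complete to the date of last survival contact. An unrecorded first therapy would make events other than death possible.

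PFS2 is an additional analysis for the Final CSR and is not in the testing hierarchy in section 1.6 of the primary SAP. Type I error, the primary PFS result and the tested secondary endpoints are unaffected.

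One ambiguity remains. The wording leaves open whether the no-subsequent-therapy condition also applies to subjects without a baseline assessment. If it does not, such a subject could start therapy, be followed afterwards and still be assigned day 0.

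**What to change.** Revise the last censoring paragraph of section 2.1 of the Final CSR SAP as follows:

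- Keep the existing conditions for censoring at randomization and add two: the subject has no PFS2 event, and no survival status is available after randomization.
- State that all other event-free subjects follow the general rule ("will be censored at the later date of last available survival status and last adequate assessment"), and leave the rule for those who started therapy and have no later information as it is.
- State that death is always a PFS2 event, whatever assessments are missing.
- Say whether the no-subsequent-therapy condition also applies to subjects without a baseline assessment.

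The cost is a sentence or two in the SAP and a matching line in the derivation of the PFS2 censoring date. No new data are needed, because survival status and subsequent therapy are already collected. Reporting the number of subjects per arm censored at randomization would show whether the point had any effect.

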2.2. Prevalence of Treatment-Emergent Adverse Events (TEAEs)

The prevalence of TEAE will be analyzed for all combined arms with planned treatment of ibrutinib (Arms A+C). The summaries of disposition, demographic and baseline characteristics for Arms A+C will be presented.

The summaries of exposure, TEAEs, and laboratory data will be presented by ibrutinib exposure intervals of 0-1 year, 1-2 years, 2-3 years, 3-4 years, 4-5 years, and >5 years (may be adjusted based on the actual data to ensure there are relatively enough subjects in the highest yearly interval) and overall.

- The exposure summary table will be presented by the actual time on ibrutinib treatment during each yearly interval.
- The TEAEs summaries (excluding TEAEs leading to deaths and other malignancies) will be presented by ibrutinib treatment duration yearly intervals and included an additional period of up to 30 days after the last dose following discontinuation of ibrutinib to cover the treatment-emergent period.
- All TEAEs leading to deaths will be presented by yearly intervals of study duration.
- Other malignancies will be presented by yearly intervals of study duration, which includes time on study to capture events that occurred after discontinuation of ibrutinib (i.e. beyond the 30-day window).

Note that the lower limit of the yearly interval will be included in the previous interval and the upper limit will be included in the current interval (e.g., a TEAE, laboratory finding, or exposure duration ending at exactly 4 years will be included in the yearly interval 3- 4 years but not the interval 4-5 years). For the determination of period prevalence, TEAEs still ongoing from the previous exposure period year will be included in addition to newly occurring TEAEs in the respective time period. Multiple events of the same preferred term (PT) within the same yearly interval for a subject will be counted only once. Prevalence of a specific TEAE during an interval will be computed from the ratio of all subjects with reported events (continuing from previous yearly interval or new onset in the interval) and the number of subjects whose TEAE period is covering the yearly interval (the end of the TEAE period is later than the beginning of the interval).

Prevalence rates of TEAEs in the overall column will be computed from all subjects who reported at least one occurrence of the specific event during the study.

The plots of diastolic blood pressure and systolic blood pressure over the time for subjects with serious hypertension will be provided.

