1.1. Study Design

This is a randomized, placebo-controlled, double-blind, Phase 3 study designed to evaluate whether treatment with ibrutinib in combination with rituximab will result in an improvement in progression-free survival (PFS) compared to placebo in combination with rituximab in subjects with WM (untreated and previously treated). In addition, an open-label ibrutinib substudy is included to further investigate the safety and efficacy of ibrutinib monotherapy in subjects with WM who are considered refractory to the last prior rituximab-containing therapy.

A total of 150 subjects were randomized in a 1:1 ratio to receive ibrutinib and rituximab (Treatment Arm A) or placebo and rituximab (Treatment Arm B). 31 subjects were enrolled in the open-label ibrutinib monotherapy substudy (Treatment Arm C). All subjects in Arm A and Arm B are to receive intravenous rituximab 375 mg/m² once weekly for 4 consecutive weeks, followed by a second 4-weekly rituximab course after a 3-month interval. In addition, all subjects in Arm A and Arm B, per randomization, are to receive oral study drug (420 mg ibrutinib or matching placebo), administered once daily and continuously until criteria for permanent discontinuation of study drug are met. All subjects in Arm C are to receive oral ibrutinib 420 mg, administered once daily and continuously until criteria for permanent discontinuation of study drug are met.

The study includes a Screening Phase, Treatment Phase and a Follow-Up Phase. All subjects are to be followed for disease progression until a PFS event occurs or until the data cutoff for final analysis.

Access to ibrutinib (cross-over) as next-line therapy for subjects with Independent Review Committee (IRC) confirmed disease progression and treated with placebo in combination with rituximab (Arm B) are provided as outlined in the protocol. Subjects who have symptomatic disease meeting criteria for requiring treatment may be eligible to receive ibrutinib as next-line therapy.

An IRC has been established to conduct response assessment and evaluate disease progression status centrally per the IRC charter.

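### Yearly adverse event prevalence counts a briefly observed subject as a full denominator unit, so intervals cut short by study end can show an artefactual fall or a blunted rise

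*SAP*

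**What the plan says.** Section 2.2 of the Final CSR SAP summarises adverse events for "all combined arms with planned treatment of ibrutinib (Arms A+C"), by "ibrutinib exposure intervals of 0-1 year, 1-2 years, 2-3 years, 3-4 years, 4-5 years, and >5 years". The rule for each interval has these parts:

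- **Numerator:** "all subjects with reported events (continuing from previous yearly interval or new onset in the interval").
- **Denominator:** "number of subjects whose TEAE period is covering the yearly interval (the end of the TEAE period is later than the beginning" of the interval). No minimum time in the interval is required.
- **Tail:** the summaries include "an additional period of up to 30 days after the last dose following discontinuation of ibrutinib to cover the treatment-emergent period".
- **Permitted change:** the intervals "may be adjusted based on the actual data to ensure there are relatively enough subjects in the highest yearly interval". The criterion is the number of subjects, not the time they were observed.
- **Time observed:** "The exposure summary table will be presented by the actual time on ibrutinib treatment during each yearly interval". This is a separate table and does not enter the prevalence ratio.

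In the appendix, Table 1 applies the same at-risk count to the new-onset tables for hypertension and for other malignancies. Neither the Final CSR SAP nor section 4.2 of the primary SAP (version 2.0) specifies a person-time denominator or an exposure-adjusted rate.

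**The concern.** These tables exist to show how toxicity changes over years on ibrutinib, so a reader will compare one interval with the next. That comparison needs roughly equal observation per counted subject, and the rule does not secure it.

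Entry was staggered and the study ends on one date. The disposition row of Table 1 expects some subjects to be continuing ibrutinib through rollover, so subjects still on drug are cut off administratively. Short coverage then collects in the last intervals, which are the ones used to judge long-term tolerability. New events have less time to occur there, while each subject still counts as one. The new-onset tables carry no ongoing events forward, so they take the full effect.

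**Working it through.** The plan states no yearly prevalence, so there is no figure to reproduce. The check asks what the stated rule returns when the true event rate is constant.

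**Inputs from the documents**
- Study end is about 3 years after the last randomization (protocol 3.1).
- Entry takes 150 / 12 = 12.5 months (protocol 10.5), or about 1.5 years (protocol 3.1).
- The tail is 30 days after last dose.
- The pool is about 75 subjects in Arm A plus Arm C, where "31 subjects were enrolled in the open-label ibrutinib monotherapy substudy": about 106 in all.

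**Assumptions not in the documents**
- Short events at a constant rate L per year.
- Exponential time on drug with a median of 30 months. This borrows the hypothesised Arm A median PFS (protocol 10.5), which is not a treatment duration and does not cover Arm C.

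**Formula.** A subject observed for c months of an interval has probability 1 - exp(-L × c/12) of a new event. The tabulated figure is the mean of this over everyone who enters the interval.

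**One subject, L = 0.3**
- Full year: 1 - exp(-0.3) = 25.9%.
- One day: 1 - exp(-0.3/365.25) = 0.08%.
- Coverage uniform over the year: 1 - (1 - exp(-0.3))/0.3 = 13.6%.

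Each of these subjects adds 1 to the denominator.

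**Whole cohort by simulation, 12.5-month entry, close at month 48.5**

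| Interval | Mean months observed | L = 0.1 | L = 0.3 | L = 0.6 |
|---|---|---|---|---|
| 0-1 | 10.7 | 8.5% | 23.3% | 40.8% |
| 1-2 | 10.5 | 8.3% | 22.8% | 39.9% |
| 2-3 | 10.5 | 8.3% | 22.8% | 39.9% |
| 3-4 | 5.7 | 4.6% | 12.9% | 23.6% |

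The apparent relative fall from year 2-3 to year 3-4 is 1 - 4.6/8.3 = 45%, 1 - 12.9/22.8 = 43% and 1 - 23.6/39.9 = 41%. With 1.5-year entry and L = 0.3, year 3-4 is about 16%, a fall of 1 - 16.0/22.8 = 30%. With a 60-month median on drug and 12.5-month entry, the series is 24.6, 24.3, 24.3, then 13.5%, so the drop does not hinge on the 30 months.

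**Event duration** (1.5-year entry, 10% per year discontinuation assumed; mean coverage 0.96, 0.95, 0.95, 0.64 and 0.25 years)

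| Event type | 0-1 | 1-2 | 2-3 | 3-4 | 4-5 |
|---|---|---|---|---|---|
| 14 days, 0.3/year | 25.0% | 25.7% | 25.5% | 18.1% | 8.1% |
| 6 months, 0.3/year | 25.1% | 34.0% | 35.4% | 28.8% | 19.9% |
| Permanent, 0.1/year | 9.0% | 17.7% | 25.6% | 30.7% | 35.1% |

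Permanent events rise throughout, but less than they should: when follow-up is long enough to leave year 3-4 untruncated, that cell is 32.7% rather than 30.7%. For the 14-day events, new onsets per 100 person-years stay at 30.1, 30.2, 29.9, 30.1 and 30.0, which recovers the constant rate.

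**Data cut** (12.5-month entry, 30-month median, L = 0.3)
- Assumed close at month 72.5: years 3-4 and 4-5 are both 22.8%, and the interval above 5 years is 12.9%.
- Assumed close at month 84.5: the interval above 5 years averages 14.8 months of coverage and rises to about 30%.

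**The case against.** A reader might infer that the tables will show a sharp false decline in the highest interval and so support a claim of improving tolerability. The documents do not support that, for three reasons.

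- Events still ongoing from the previous year are carried into the numerator. Persistent events therefore show a blunted rise, and even six-month events are higher in year 3-4 (28.8%) than in year 0-1 (25.1%).
- The place and size of any drop depend on a data cut the documents do not state. On the protocol's timing the longest possible follow-up is 3 + 1.5 = 4.5 years, yet the SAP plans intervals of 4-5 and above 5 years, so it evidently expects a later cut. The last interval has no upper bound and can be inflated as easily as deflated.
- Nowhere do the documents claim that tolerability improves.

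It is also fair to say that the measure is labelled a period prevalence, that exposure per interval is tabulated, and that the highest interval may be adjusted. These points narrow the concern without removing it. A separate exposure table lets a reader suspect short coverage but leaves the ratio uncorrected. The permitted adjustment responds to subject counts, not observation time.

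One tempting remedy would do harm. Dividing all subjects with an event by patient-months, carried-over events included, creates the opposite artefact. A steady 30% prevalence gives 30/10.5 = 2.9 per 100 patient-months in year 2-3 and 30/5.7 = 5.3 in year 3-4, an apparent rise of 84%.

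**Conclusion.** The concern holds in a conditional form. The denominator ignores time observed, and no planned measure corrects for it. Where study end truncates an interval, resolving or new-onset events can fall artefactually and persistent events can rise too little, at constant risk. The interval above 5 years is not a one-year period and is not comparable with the others in either direction.

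For short events the illustrated relative fall is 41-45% with 12.5-month entry and about 30% with 1.5-year entry (L = 0.3). These sizes rest on assumed event rates, durations and time on drug, and on closing 3 years after last entry; they are not predictions for this trial. The analysis is descriptive, so what is at stake is the reading of long-term safety.

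**What to change.** Keep the period-prevalence table and add three things to section 2.2 and Table 1 of the Final CSR SAP:

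1. Exposure-adjusted new-onset rates per 100 patient-months or patient-years observed in each interval, counting new onsets only and excluding carried-over events. Include the hypertension and other-malignancy tables. Use TEAE-period person-time for on-treatment tables and time on study for tables by study duration.
2. Mean months observed per interval, including the interval above 5 years, printed beside each prevalence figure.
3. A statement that intervals whose mean coverage differs materially from 12 months are not read as part of a time trend.

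The cost is SAP wording and a small amount of extra tabulation. Most of the person-time comes from the exposure-by-interval summary already planned, with the post-treatment tail added. The new rates supplement the prevalence of ongoing events and do not replace it.
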